Appendix B

GEL APPLICATION INSTRUCTIONS

1. Flammable: do not apply near fire, flame or heat, or while smoking
2. Apply the gel to your breast after bathing, preferably in the morning and at approximately the same time each day. Apply approximately 30 minutes after bathing when breast is completely dry.
3. To apply, remove the cap from the bottle. When you use the bottle for the first time, you must prime it by pressing the pump fully several times until gel is dispensed (point the spout toward a sink or wastebasket and do not use the first dose, which may be incorrect).
4. Once the bottle is primed, hold it in one hand and place the palm of your other hand under the pump to catch the gel. Be sure to press down completely on the pump and release it completely to dispense one dose of gel.
5. Apply **one dose of gel to one breast** (dosage is indicated on the bottle label). Do not apply more or less than one dose to the breast. If you are assigned to the 20mg dose level (which requires two (2) pumps), be sure to release the pump completely between both actuations (pumps). Application of gel will always be to only one breast and the same breast each time. Do not alternate doses between breasts.
6. If you accidentally pump more than is needed, please discard this dose and try again to get the correct dose. If you do discard pumped doses, please record this on your Gel Diary.
7. Spread the gel evenly over the upper outer and upper inner quadrant of your breast, without rubbing. Start from above the areola and spread outwards to below the clavicle and up to the midsternal edge which is the midline of your chest. Avoid spreading the gel in the nipple and areola area of the breast. Avoid spreading the gel below the nipple or underneath the breast. Please see diagram below.

8. Wash your hands immediately after applying the gel.
9. Allow the gel on your breast to air dry for 2 minutes and then immediately cover with clothing (the gel is colorless and will not stain your clothing). Do not expose your bare breasts to sunlight or ultraviolet light (tanning beds) at any time while on the study.
10. Do not apply any other cream, lotion or moisturizer to your breast immediately after application of the study drug.
11. Do not wash your breast or immerse in water (bath, swim) for at least 4 hours following application of the

gel. If this is not possible, delay application of the gel that day until after immersion, and be sure to follow all the above instructions. If you regularly swim in the morning, it is better to apply the gel afterwards, after your shower.

12. After use, replace the cap on the bottle.

RECOMMENDATIONS:

1. Be sure to apply **after bathing or showering, each day** during the study and preferably in the morning.
2. You may use CeraVe moisturizing cream, a moisturizer that will be supplied to you, to apply to the same breast that you are applying the study gel. CeraVe moisturizing cream can be used in the evening or at least 4 hours after study gel application so it will not interfere with absorption. CeraVe moisturizing cream can be applied daily to help with any skin redness.
3. If you forget to apply a dose, do not double the dose to “catch up”.

If you are applying the gel **daily**: If your next dose is scheduled within the next 12 hours, it is best just to wait; if it is more than 12 hours until your next dose, apply the dose you missed and resume your normal dosing after that.

If you are applying the gel **every other day**: If your next dose is scheduled within the next 24 hours, it is best just to wait; if it is more than 24 hours until your next dose, apply the dose you missed and resume your normal dosing after that.

4. For the duration of the study, avoid contact between the application area and the skin of other individuals (i.e. your child, your sexual partner, or other persons). If necessary, skin contact is allowable after the breast has been washed. As noted above, you must wait at least 4 hours following application before washing the application area, otherwise, delay application until after washing and contact.
5. Avoid using sprays containing DEET (i.e. bug spray) to the treated area and limit vitamin A intake to <5000 IU per day.
6. Do not ingest or swallow the gel. For external use only.
7. Please note the first and last day of use on the bottle label.
8. If the pump doesn't come back up correctly or if there's no gel delivered when you press down on the pump, notify your doctor immediately. A replacement bottle will be shipped to you.
9. After the end of study treatment, be sure to take back to your doctor **all** the gel bottles you have been given (even if empty or not used). **This is very important for the success of the study.**
10. If any ulcerations, blisters or open areas start please notify the research team the next day for guidance.

STORAGE INSTRUCTIONS:

1. Keep your gel bottles in a cool room temperature- 59°F to 77°F.
2. Keep the gel bottles out of the reach of children.

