Bexarotene gel will be provided by Valeant pharmaceuticals and repackaged by DCP pharmacy in dose metered pumps for dispensing the correct dose for application. Participants will begin application of the gel to the upper outer and upper inner quadrants of one breast every other day for one week and then increase to daily for 3 weeks if they are assigned to daily dosing arm. If participants are assigned to every other day dosing, they will continue in this manner for the entire 4 weeks. Participants that are assigned to 20 mg (2ml) daily will first start with application of 10mg (1ml) to the breast every other day for 1 week, then increase to 10mg (1ml) daily for 1 week, and then increase to 20mg (2ml) daily for the remaining 2 weeks as long as it is tolerated. Participants can also participate in an optional core breast biopsy of the upper outer or inner quadrant at the end of study treatment and receive compensation for additional expenses associated with the biopsy, such as additional travel expenses, time missed from work or other expenses associated with the biopsy visit. All participants will need

to come in for clinic visits for toxicity assessment and blood collection. All participants will receive a follow-up phone call from the site investigator or designee 30 days \pm 7 days after completion of study drug to assess for any further AE and document resolution of any acquired AE during treatment.

As of Oct 2019, enrollment was completed to the first dose cohort and the second dose cohort was stopped early due to DLTs. No DLTs were experienced in the first dose cohort of 10 patients that applied 10mg of bexarotene to the breast every other day. In the second dose cohort, participants applied 10mg daily after tolerating application of every other day for one week. Four participants were enrolled in this cohort and 1 participant withdrew early due to adverse events unrelated to study drug. Two DLTs were noted in the remaining patients and thus enrollment was stopped at the second dose level. Therefore, no patients will be enrolled to the third dose level due to concerns for toxicity. MTD is 10mg/breast/every other day.

B. Dose Expansion Group

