5.2 Gel Administration/Run-in Procedures

Each Bexarotene gel canister will contain 30 reliable doses of product metered to dispense 1mL per actuation, 1g of bexarotene gel per actuation. One gram of bexarotene gel contains 10mg of active bexarotene.

Participants in all dose levels will be instructed to apply the gel at 10mg (1 mL) every other day to one unaffected breast for the first 7 days of treatment. After the Day 8 phone call and confirmation that toxicity is at an acceptable range, participants assigned to 10mg/breast/daily will increase applications to daily. Participants assigned to 10mg/breast/every other day will continue to apply gel every other day. Participants assigned to 20mg/breast/daily will increase from 10mg (1mL) every other day to daily application for another 7 days. After the Day 15 visit and confirmation of acceptable toxicity, participants will increase to 20mg (2 mL) to the one unaffected breast daily for the remaining 2 weeks. All participants will continue to apply the gel to one unaffected breast as directed for a duration of 4 weeks. Participants in the dose expansion group will apply the gel with the same ramp up schedule as those in the dose escalation group for that dose level.

Participants will also receive moisturizing lotion [CeraVe] that can be applied to the breast to reduce and prevent redness that can be related from the study drug. CeraVe will be provided to all participants and they will be instructed to apply to the treated breast in the evening or at least 4 hours after application of study drug so it will not interfere with the absorption of study drug.

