- Participants need to have had any breast imaging with a normal/benign (bi-rads 1 or 2) result within 180 days of Day 0 and no further routine breast imaging planned during the course of the study (4 weeks). Exception: if the mammogram result was a bi-rads 0 and the imaging work-up (ultrasound and/or MRI) result comes back normal/benign (bi-rads 1 or 2) before treatment initiation, then participant is eligible.
 - Tobacco and Alcohol Use Assessment, using the Baseline questionnaires. See Appendix D “Alcohol and Tobacco Use Assessment Questionnaires – Baseline”. Refer to Appendix F for resources for alcohol and tobacco quitting. These resources can be given to individuals if there is concern about alcohol or tobacco dependence. It is not expected that investigators will refer individuals for assistance or that they will undertake the care of individuals for alcohol or tobacco dependence.
 - Confirm eligibility: At the completion of the screening period, eligibility must be confirmed. Only after eligibility is confirmed, eligible participants can be assigned to a dose level and scheduled for the on study tests and procedures.

Day 0

The following procedures will be conducted on Day 0:

- For women of childbearing potential a pregnancy test must be completed within 72 hours prior to or on Day 0. Either a serum or urine pregnancy test may be performed. If a urine pregnancy test is performed, the test must be done in the clinic or in the lab:
 - If pregnancy test result is positive on Day 0, do not dispense drug, take participant off-study, complete the Off-Study Case Report Form (CRF), follow the pregnancy to term and complete the Outcome of Pregnancy Case Report Form (CRF).
 - If a pregnancy is discovered after Day 0, instruct the participant to stop taking drug, take participant off-study, complete the Off-Study CRF, follow the pregnancy to term and complete the Outcome of Pregnancy CRF.
 - Study drug should be initiated on the second or third day of a normal menstrual period.
- Research Blood Sample for serum bexarotene concentration.
-
- Depending on the dose assignment, participants will receive:
 - Bexarotene 1 % gel 10mg/breast/every other day x 4 weeks
 - Bexarotene 1% gel 10mg/breast/daily x 4 weeks
 - Bexarotene 1% gel 20mg/breast/daily x 4 weeks
- Review guidelines for gel application with the participant.
- Review Gel Diary with the participant (see Appendix C). Provide instructions on use of diary.

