	Day	Date	R or L Breast	Initials	# of pumps	Did you experience any symptoms, if "Yes" list below List # of discarded doses here
Week 1 Apply 1 pump to the breast every other day	1				___ or  Did not apply	
	2				___ or  Did not apply	
	3				___ or  Did not apply	
	4				___ or  Did not apply	
	5				___ or  Did not apply	
	6				___ or  Did not apply	
	7				___ or  Did not apply	
Week 2 Apply 1 pump to the breast every day	8				___ or  Did not apply	
	9				___ or  Did not apply	
	10				___ or  Did not apply	
	11				___ or  Did not apply	
	12				___ or  Did not apply	
	13				___ or  Did not apply	
	14				___ or  Did not apply	
Week 3 Apply 2 pumps to the breast every day	15				___ or  Did not apply	
	16				___ or  Did not apply	
	17				___ or  Did not apply	
	18				___ or  Did not apply	
	19				___ or  Did not apply	
	20				___ or  Did not apply	
	21				___ or  Did not apply	

	Day	Date	R or L Breast	Initials	# of pumps	Did you experience any symptoms, if "Yes" list below List # of discarded doses here
Week 4 Apply 2 pumps to the breast every day	22				_____ or  Did not apply	
	23				_____ or  Did not apply	
	24				_____ or  Did not apply	
	25				_____ or  Did not apply	
	26				_____ or  Did not apply	
	27				_____ or  Did not apply	
	28				_____ or  Did not apply	
	29				_____ or  Did not apply	
	30				_____ or  Did not apply	

Participant's Signature: _____

Date: _____

Reviewer's Signature: _____

Date: _____

Comments:

Bexarotene Gel Diary [IRB Protocol #:]

Dose Expansion Group

PID: _____

Amount of Agent Provided: Number of Canisters _____

Total Daily Dose: 10mg applied to one breast, **every other day**

Pump actuations: Push the Pump 1 time

Breast to Apply Gel: Right OR Left

Number of Canisters Returned: _____

Visit#: _____

INSTRUCTIONS:

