
1. Complete the diary daily.
2. If you miss an application, do not take an extra application to “make up” for the missed application.

If your next dose is scheduled within the next 24 hours, it is best just to wait; if it is more than 24 hours until your next dose, apply the dose you missed and resume your normal dosing after that.
3. If you accidentally pump more than is needed for one breast, please discard this dose and try again to get correct dose. If you do discard pumped doses, please record this on your Gel Diary.
4. Do not discard the gel canister. Bring the canister and this diary to your next appointment.
5. Store the study gel at home at room temperature and avoid extreme heat or cold during transportation from the clinic to home.
6. If you experience any concerning side effects or changes in the texture of your skin (e.g., skin feels like sandpaper), call _____ (insert name of Study Coordinator or Study Nurse) at _____ (insert telephone number) or the study doctor, [name] at [contact] for guidance.

Bexarotene Gel Diary: Dose Expansion Group (Continued)

Please Bring this Sheet and Empty Canister to Your Next Visit

	Day	Date	R or L Breast, OR Did not apply	Initials	Did you experience any symptoms, if "Yes" list below List # of discarded pumps of gel here
Week 1 Apply 1 pump to the breast every other day	1		 R  L  Did not apply		
	2		 R  L  Did not apply		
	3		 R  L  Did not apply		
	4		 R  L  Did not apply		
	5		 R  L  Did not apply		
	6		 R  L  Did not apply		
	7		 R  L  Did not apply		
Week 2 Apply 1 pump to the breast every other day	8		 R  L  Did not apply		
	9		 R  L  Did not apply		
	10		 R  L  Did not apply		
	11		 R  L  Did not apply		

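### Appendix B, Recommendation 1 tells every participant to apply the gel each day, but the only regimen still open is every other day

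*Combined protocol and SAP*

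**What the plan says.** Section 5.1 points to Appendix B as the place for detailed application instructions. Item 1 under Recommendations in that appendix, which is not limited to any dose group, reads "Be sure to apply after bathing or showering, each day during the study and preferably in the morning". The words about bathing and daily application are in bold.

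The rest of the document sets a different frequency:

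- Section 3, part A: "MTD is 10mg/breast/every other day". On the 10 mg daily level it reports "Two DLTs were noted in the remaining patients and thus enrollment was stopped at the second dose level". The 20 mg level was never opened. The expansion group of 10, treated at the maximum tolerated dose (MTD), is therefore the only regimen still open.
- Section 5.2, for the first 7 days: "Participants in all dose levels will be instructed to apply the gel at 10mg (1 mL) every other day to one unaffected breast". The every-other-day group then stays on that schedule.
- Appendix C, expansion-group diary, header: "Total Daily Dose: 10mg applied to one breast, every other day". The weekly blocks agree, for example "Week 2 Apply 1 pump to the breast every other day".

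The handout itself allows for alternate-day users. Recommendation 3 has a separate missed-dose rule that begins "If you are applying the gel every other day".

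**The concern.** Appendix B goes home with the participant and tells her how to use the drug. One of its lines gives a frequency that is wrong for everyone in the first week and wrong throughout for the expansion group. The frequency it names is the one at which escalation stopped: four women were enrolled at 10 mg daily, one withdrew for events unrelated to the drug, and two of the remaining three had DLTs.

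The stake is a small, avoidable safety risk to a healthy volunteer. There is also a possible effect on the data. With ten women in the expansion group, a DLT or a tissue concentration produced by unintended daily use would be attributed to the every-other-day dose.

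**Working it through.** The plan gives no figure on this point to reproduce. The check compares the instructions and then counts applications under each reading.

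**Instructions side by side**

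| Source | Week 1 | Weeks 2–4, expansion group |
|---|---|---|
| Appendix B, Recommendation 1 | each day | each day |
| Section 5.2 | every other day, all levels | every other day |
| Section 3 (MTD) | every other day | every other day |
| Appendix C, expansion diary | every other day | every other day |

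Read literally, Recommendation 1 differs from every other source, and in Week 1 it fits no dose group.

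**Inputs.** Dosing starts on Day 1 (Section 7.3). Each application is 10 mg and treatment runs for 28 days (Sections 3 and 5.2). Contacts are the Day 8 call and the Day 15 visit, each ±2 days (Section 7.1). Assumptions: every other day means odd-numbered days, and doses are counted through the day before the contact.

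**Extra applications = daily count − every-other-day count**

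| Caught at | Daily | Every other day | Extra |
|---|---|---|---|
| Day 8 call, held on Day 6 | 5 | 3 | 2 |
| Day 8 call, held on Day 8 | 7 | 4 | 3 |
| Day 8 call, held on Day 10 | 9 | 5 | 4 |
| Day 15 visit, held on Day 13 | 12 | 6 | 6 |
| Day 15 visit, held on Day 15 | 14 | 7 | 7 |
| Day 15 visit, held on Day 17 | 16 | 8 | 8 |
| Never caught, Days 1–28 | 28 | 14 | 14 |

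**Total drug over 28 days**

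- Every other day: 14 × 10 mg = 140 mg.
- Literal daily use: 28 × 10 mg = 280 mg, and 280 / 140 = 2.0 times the intended amount.
- Closed 10 mg daily level with its ramp-up: 4 applications in Week 1 + 21 on Days 8–28 = 25, or 250 mg. Literal daily use slightly exceeds this because it skips the ramp-up.

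**Sensitivity.** Note f to the schedule in Section 7.1 asks for the last dose on Day 28. If that adds a dose to the odd-day schedule, the intended count is 15 and the largest excess is 28 − 15 = 13.

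**Would anything physically stop the error?** No. A canister holds 30 reliable doses (Section 5.2), so 28 daily applications need not exhaust it. The label contents in Section 6.6 do not include frequency. The diary has an application box for every day, so daily use could be recorded without meeting a blocked row.

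**The case against.** The strongest reply is that the sentence does not set frequency at all. It is about time of day and bathing, it appears under Recommendations after the numbered instructions, and Recommendation 3 would make no sense if every woman applied the gel daily. Frequency is set in the diary, which states it correctly in the header and in all four weekly blocks and offers a box for days without an application. Application is demonstrated in clinic (Section 5.1). On Day 0 staff must "Review guidelines for gel application with the participant" and go through the diary with her (Section 7.2), and the diary is reviewed again at Days 8 and 15 (Section 7.3). The ten women in the first cohort are reported to have applied the gel every other day without a DLT. On this view the point is a copy-edit, and the excess-dose counts describe someone who ignores everything else she was given.

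Most of this stands. The line is not evidence of a different planned schedule, and the counts are conditional: the documents give no basis for a probability of misdosing. Item 2 of the same appendix, which also mentions each day, really is time-of-day advice and is not counted here. What does not stand is the step from unlikely to correct. Recommendation 1 tells her to be sure to apply, and puts the daily wording in bold. The Day 8 and Day 15 reviews would find an error only after extra doses had been applied. A dosing instruction should not need other documents to correct it.

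**Conclusion.** The inconsistency is real and minor. As written, Recommendation 1 conflicts with the every-other-day MTD, with the first week at every dose level, and with the expansion diary. If one woman followed it alone, the likely excess is 3 applications (2 to 4 across the window) if caught at the Day 8 call, or 7 (6 to 8) if caught at Day 15. The worst case is 14 extra applications, or 13 if the Day 28 dose is added to the schedule, and it requires her to disregard all four diary blocks and two diary reviews to miss it.

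These counts rest on a Day 1 start, odd-day dosing and 10 mg per application. The DLT definition, stopping boundaries, MTD and planned analyses are unaffected. Confidence is high, because the conflict can be read directly from the text.

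**What to change.** In Appendix B, Recommendation 1, replace *each day* with *on each scheduled application day shown in your Gel Diary*. For the expansion group that means every other day. The wording suits every dose group and points to a document that is already right. Item 2 of the application instructions can be aligned in the same edit, though this is optional.

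The cost is one line in a participant handout at the next amendment. No participants, visits, procedures or analyses change.

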5.5 Dose Modification

For any grade 1 adverse events or grade 2 adverse events that are not hypertriglyceridemia or skin related, no dose modifications will be made. For any grade 2 skin toxicity possibly, probably, or definitely related to study drug that persists for 3 days, drug will be held for 3 days. Participants at the lowest dose level will restart gel application at every 3 days dosing for 3 days (1 dose) and then increase back to every other day dosing. If grade 2 skin toxicity recurs and persists for 3 days, drug application will be discontinued and will be classified as a DLT. Participants in the second dose level (10mg daily) will hold for 3 days if toxicity is noted and resume at 10mg every other day for 4 days (2 doses) and then increase back to daily dosing. Participants at the highest dose level (20mg daily) will hold for 3 days and resume at 10mg daily for 3 days (3 doses) and then increase back to 20mg daily. Participants experiencing Grade 3 or Grade 4 toxicities of any attribution will be taken off study drug. Please see Table 1 for dose modification algorithm.

Table 1: Dose Modification Algorithm for Grade 2 Skin Adverse Events related to Bexarotene Gel

Dose Level	If Grade 2 Skin AE Persists for 3 Days	Dose Modification (If Skin AE resolves to \leq Grade 1)	If Grade 2 Skin AE Recurs and Persists for 3 Days
10mg/breast/every other day	Hold Study Drug for 3 days	Restart drug application at 10mg/breast/every three days for 3 days (1 dose) and then increase to original dose	Stop Drug
10mg/breast/daily	Hold Study Drug for 3 days	Restart drug application at 10mg/breast/every other day for 4 days (2 doses) and then increase to original dose	Stop Drug
20mg/breast/daily	Hold Study Drug for 3 days	Restart drug at 10mg/breast/ daily for 3 days (3 doses) and then increase to original dose	Stop Drug

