 - If a pregnancy is discovered after Day 0, instruct the participant to stop applying the gel, take participant off-study, complete the Off-Study CRF, follow the pregnancy to term and complete the Outcome of Pregnancy CRF.
- d) Research blood sample for serum bexarotene level.
- e) Participants need to have had any breast imaging with a normal/benign (bi-rads 1 or 2) result within 180 days of Day 0 and no further routine breast imaging planned during the course of the study (4 weeks). Exception: if the mammogram result was a bi-rads 0 and the imaging work-up (ultrasound and/or MRI) result comes back normal/benign (bi-rads 1 or 2) before treatment initiation, then participant is eligible.
- f) Participants must be instructed to apply the last dose of their study medication on the last day of the study (Day 28).
- g) Dermatology evaluation within 72 hours of study visit if participant experiences a grade 3 skin event or continues to have a persistent grade 2 skin event despite dose modification.
- h) The core biopsy at Day 28 is optional for dose escalation cohort participants. The biopsy is mandatory for participants in the dose expansion cohort at Day 28. If the participant is on aspirin, non-steroidal anti-inflammatory drugs or Vitamin E, she will be instructed to discontinue these 7 days prior to the end of treatment biopsy.
- i) See Appendix D “Alcohol and Tobacco Use Assessment Questionnaires – Baseline”.
- j) See Appendix E “Alcohol and Tobacco Use Assessment Questionnaires – Follow Up”.

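### A participant with an ulcer, blister or open area is told to report it the next day and is not told to withhold the next dose, so gel can go on broken skin before staff have graded it

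*Combined protocol and SAP*

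**What the plan says.** Appendix B, Recommendations item 10, is the only participant instruction that names open lesions: "If any ulcerations, blisters or open areas start please notify the research team the next day for guidance". It does not mention the next application.

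Item 6 of the Dose Expansion Group diary (Appendix C) is broader and sets no delay: "If you experience any concerning side effects or changes in the texture of your skin (e.g., skin feels like sandpaper), call" the study team for guidance. It does not mention the next application either.

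The rest of the participant material keeps dosing going. The diary calendar reads "Apply 1 pump to the breast every other day". Appendix B item 2 says "Apply the gel to your breast after bathing, preferably in the morning and at approximately the same time each day". The missed-dose rule is "if it is more than 24 hours until your next dose, apply the dose you missed and resume your normal dosing after that". Footnote f of the Schedule of Events (7.1) asks for the last dose on Day 28.

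The protocol body speaks to staff:
- 4.2.9 excludes women with broken skin at entry.
- 5.3 says women whose skin condition causes breakdown should not use the gel.
- 5.5 and 8.3 take Grade 3 or 4 events off drug.
- Below that, 5.5 acts by grade: "For any grade 1 adverse events or grade 2 adverse events that are not hypertriglyceridemia or skin related, no dose modifications will be made". A related Grade 2 skin event "that persists for 3 days, drug will be held for 3 days".

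**The concern.** The gel is self-applied at home, and the off-drug and hold rules work only once staff know of a lesion and have graded it. The participant's sheet covers the time before that. For the lesions it names, it sets a next-day report and leaves the next dose in place. Appendix B item 8, on a faulty pump, asks for immediate notification, so the less serious problem gets the faster report.

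Some of these lesions could be events for which the protocol stops the drug. In the photosensitivity row of Table 3 (8.1), blistering or skin breakdown with erythema is Grade 3 and ulceration with erythema is Grade 4. At the Day 15 visit a Grade 3 finding means the drug is held (7.3). At home the sheet has no matching step.

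The sheet matters most after Day 15, because the next routine contact is Day 28. What is at stake is participant safety in a trial whose primary endpoint is safety. No error rate or sample size is affected.

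**Working it through.** The plan gives no figure to reproduce. The check counts the applications that can fall between onset and first contact with staff.

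**Inputs.** The dose is 10 mg every other day (Section 3 and the expansion diary). Treatment starts on Day 1 (7.3), the call is due the day after onset (Appendix B item 10), and a Day 28 last dose is possible (7.1 footnote f).

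**Assumptions.** She keeps the schedule and makes only the next-day call. Where a dose and the call fall on the same day, she doses first. She receives guidance on that call, before any later dose.

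**Schedule.** Days 1, 3, ..., 27 give 14 applications, or 15 if a Day 28 dose is added.

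| Onset on day d | Next application | Call due | Doses before contact |
|---|---|---|---|
| Off-day | d+1 | d+1 | 1 |
| Dosing day, before application | d, then d+2 | d+1 | 1 |
| Dosing day, after application | d+2 | d+1 | 0 |
| Day 27, after application, Day 28 dose given | Day 28 | Day 28 | 1 |
| Day 27, before application, Day 28 dose given | Days 27 and 28 | Day 28 | 2 |

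The usual exposure is therefore one dose of 10 mg. The last row gives 20 mg. That row is an edge case, since Day 28 is nominally the clinic visit.

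**Contact gap after Day 15.** 28 − 15 = 13 days. With both ±2-day windows, the range is 26 − 17 = 9 to 30 − 13 = 17 days. Conditional contacts can fall inside it: triglyceride monitoring or a recheck (5.5), and a dermatology evaluation (footnote g).

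**Dose cost of waiting for a call.** If a dose is due at time T, the next is due at T + 48 h. If staff clear her before T + 24 h, more than 24 h remain, so the missed-dose rule lets her apply late and no dose is lost. If they clear her later, one dose is lost.

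**Compliance, against the 75% limit in 5.6.1.**
- One dose skipped: 13/14 = 92.9%, or 14/15 = 93.3%.
- Three skipped: 11/14 = 78.6%, or 12/15 = 80.0%.
- Four skipped: 10/14 = 71.4%, or 11/15 = 73.3%, below the limit.

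If dosing follows the ±2-day Day 28 window (an assumption), totals run from 13 to 16. One skipped dose then leaves 12/13 = 92.3% to 15/16 = 93.8%.

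**The case against.** The best defence is that the plan already covers most of this. Diary item 6 invites a call about any concerning side effect with no delay, and an ulcer or blister plainly qualifies. Section 8.1 has her outline reddened areas and report changes, and gel use is demonstrated and reviewed with her before treatment starts. An extra dose needs unfavourable timing and a woman who sees open skin, does not use item 6, and doses before calling. Much of this stands and it lowers the likelihood. It does not supply the missing words about the next dose, and item 10 is the more specific instruction for these lesions. Reading item 10 as a deadline of the next day leaves the same gap.

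The second defence is that on treatment the protocol acts by grade and accepts dosing during a Grade 2 skin event until it has lasted 3 days. That is correct, and it limits what can be claimed. A reader might infer that item 10 contradicts 4.2.9 or 5.3. It does not: 4.2.9 is an entry rule, and 5.3 does not expressly name new lesions on treatment. A reader might also infer that every blister is Grade 3, but that grade stands only in the photosensitivity row of Table 3.

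Third, a reader might want a new hold at any grade in 5.5. The documents do not support that as a correction. It would cut across the rule of no modification at Grade 1. It would also put the expansion participants under a different hold rule from the 10 escalation participants with whom their DLTs are pooled (8.1, 13.4).

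**Conclusion.** The point holds as a minor participant-safety matter of wording. At the current dose, a woman who follows the sheet and doses before calling can usually apply one more 10 mg dose to broken skin before staff grade it. The number is two in the Day 27/28 edge case, and none when onset follows application on other dosing days. This is a mismatch with the intent of 4.2.9, 5.3 and the Grade 3/4 off-drug rule.

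Frequency and harm are unknown. None of the 10 women treated at this dose had a DLT (Section 3), so none had a related event of Grade 3 or higher, but this says nothing about lesser open lesions. Up to 10 expansion women receive the sheet; it would be wrong to infer that all 10 are affected, since that needs both a lesion and the timing above. Nor is one dose an absolute ceiling, or the period from Day 15 to Day 28 always without contact. The consent pages were not part of the reviewed text, so a stop instruction there cannot be excluded.

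**What to change.** Reword Appendix B, Recommendations item 10, to say in substance: *If an ulcer, blister or open area appears, call the research team the same day and do not apply the next dose until you have spoken with them.* Add the same sentence to item 6 of the Dose Expansion Group diary. Staff then grade the lesion and continue, hold or stop under 5.5 and 8.3 as they stand. Add no new any-grade hold to 5.5. Record any delayed or skipped dose, with the reason, in the diary, which already has a box for a dose not applied.

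The cost is a small amendment needing DCP and then IRB approval (14.3), and usually at most one delayed or skipped dose. Two side effects should be acknowledged. A dose skipped near Day 28 could slightly lower that participant's tissue level, and a skipped dose could shorten a Grade 2 event that would otherwise have lasted the 6 days that make it a DLT. Any such dose should therefore be noted when expansion DLTs are pooled with those of the escalation 10.
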